4.1 Study Analysis

This single-center, single-arm, Phase I/II, trial is designed to examine the safety, tolerability and limited efficacy of human clazakizumab (25mg SC Q4W) given as per protocol (Appendix A) in 10 subjects who are DSA + and have biopsy proven cABMR + TG. Patients considered for this study may have been treated with high-dose IVIG + rituximab and/or plasmapheresis^{3,6,7} In addition, some patients with early, severe ABMR may have been treated with Eculizumab⁴².

4.2 Defining ABMR

For purposes of this investigation, antibody-mediated rejection (ABMR) is defined as follows:

- ✓ Deterioration of allograft function in a transplant recipient measured by eGFR (defined as a eGFR ≥ 30cc/min reduction from baseline).
- Association with the presence of DSA (usually increasing in strength) measured by luminex techniques.
- ✓ Biopsy evidence of cABMR and TG by biopsy by Banff 2015 criteria.

4.3 Treatment of Allograft Rejection Episodes During the Study

[figure not shown]
Biopsy-proven rejection episodes that occur during the study are treated with "pulse" methylprednisolone (10mg/kg/day, max 1000mg for >100kg for 3 days) and anti-thymocyte globulin (1.5mg/kg daily X 4) for cell-mediated rejection episodes that are unresponsive to pulse steroids. Patients experiencing recurrent ABMR episodes after study drug treatment, will initially receive pulse methylprednisolone (10mg/kg/day, max 1000mg for >100kg) IV daily x 3 doses then, depending on severity, IVIG 10% solution 2gm/kg (max 140g for >70kg) IV X1 dose followed by rituximab (375mg/m2 rounded to the nearest 100mg) IV X1 dose three to five days after last IVIG dose. In cases where rapid deterioration of allograft function is seen and/or thrombotic microangiopathy diagnosed, the patient will receive plasma exchange X 3-5 sessions followed by anti-C5 (Eculizumab®) IV weekly X4 weeks (1200mg week #1 followed by 900mg/weekly for 3 additional weeks). Efficacy of therapy will be assessed by determining renal function improvement, monitoring DSA responses and repeat allograft biopsies, if needed.

4.4 Monitoring for AE/SAEs Post-Transplant in HS Patients

Adverse events (AEs) and serious adverse events will be monitored post-ABMR treatment with clazakizumab. These include careful attention to infectious complications potentially associated with clazakizumab therapy.

Infectious complications associated with IVIG + rituximab desensitization and alemtuzumab induction therapy followed by maintenance therapy with tacrolimus, MMF and prednisone have been assessed by our group. Briefly, we evaluated 170 patients who were desensitized with IVIG + rituximab followed by alemtuzumab induction and maintenance therapy with tacrolimus, MMF and steroids. This was compared to a concomitant group of non-sensitized, low-risk transplants (N=191) who did not receive IVIG, rituximab or alemtuzumab (induction with IL-2R blockers). A careful analysis of all infections and serious infections that occurred over the next 4 years was compiled and is shown in Figure 15A &15B. Briefly, these data show that the use of this desensitization protocol followed with alemtuzumab induction does not increase the risk for common or serious infections post-transplant compared to a low risk group of patients. Serious infections were defined as any viral infection and fungal or bacterial infections requiring i.v. antibiotics or

hospitalizations⁴¹. Thus risk for infections in the study group (clazakizumab) after ABMR treatment will likely be similar and comparable to non-sensitized patients. All patients entered into this study are required to be vaccinated for *Streptococcus pneumoniae*.

15A & 15B: This figure shows the proportion of kidney transplant recipients who developed infections (all infections 15A, or serious infections 15B) post-transplant. Patients were in the low-risk group (non-Ritux #191) who did not receive IVIG/ritux or alemtuzumab or (Ritux #171) who received desensitization with rituximab, IVIG followed by transplantation. Follow up for up to 45 months shows that infection rates are similar. The commonest infection was urinary tract infection in both groups. The incidence of CMV was greater in the non-Ritux group while there were more BK infections in the Ritux group. No patients in the Ritux group developed PTLD or PML while 2 patients in the non-Ritux group developed PTLD⁴³.

More recent safety data on viral infections in more than 400 highly HLA sensitized patients treated with IVIG + rituximab and Campath-1H induction therapy were compared to ~600 patients who were non-sensitized and did not receive desensitization. The data are shown below:

[figure not shown]

Figure 16: The data shown above show the viral PCR positivity for CMV, EBV and polyma BK virus in 400 desensitized patients compared with 600 standard kidney transplant recipients. Of interest are the significantly lower incidence of EBV and CMV viremia in desensitized individuals compared with normal non-sensitized transplant recipients. No differences were seen between the highly-HLA sensitized patients and non-sensitized patients in incidence of BK viremia. Thus, no significant risk for viremia is seen, in fact, there appears to be a benefical effect of DES on reducing incidence of CMV and EBV viremia.

4.5 Safety Reporting of Adverse Events

Safety Reporting of Adverse Events

Assessment of Safety

Specification of Safety Variables

Safety assessments will consist of monitoring and reporting all adverse events (AEs) and serious adverse events (SAEs), all events of death, and any study specific issue of concern.

Adverse Events

An AE is any unfavorable and unintended sign, symptom, or disease temporally associated with the use of an investigational medicinal product (IMP) or other protocol-imposed intervention, regardless of attribution.

This includes the following:

- AEs not previously observed in the subject that emerge during the protocol-specified AE reporting period, including signs or symptoms associated with Clazakizumab infusion that were not present prior to the AE reporting period.
- Complications that occur as a result of protocol-mandated interventions (e.g., renal protocol biopsy).
- If applicable, AEs that occur prior to assignment of study treatment associated with medication washout, no treatment run-in, or other protocol-mandated intervention.
- Preexisting medical conditions (other than the condition being studied) judged by the investigator to have worsened in severity or frequency or changed in character during the protocol-specified AE reporting period.

Serious Adverse Events

An AE should be classified as an SAE if the following criteria are met:

- It results in death (i.e., the AE actually causes or leads to death).
- It is life threatening (i.e., the AE, in the view of the investigator, places the subject at immediate risk of death. It does not include an AE that, had it occurred in a more severe form, might have caused death.).
- It requires or prolongs inpatient hospitalization.
- It results in persistent or significant disability/incapacity (i.e., the AE results in substantial disruption of the subject's ability to conduct normal life functions).
- It results in a congenital anomaly/birth defect in a neonate/infant born to a mother exposed to the IMP.
- It is considered a significant medical event by the investigator based on medical judgment (e.g., may jeopardize the subject or may require medical/surgical intervention to prevent one of the outcomes listed above).

Methods and Timing for Assessing AND Recording Safety variables

The investigator is responsible for ensuring that all AEs and SAEs that are observed or reported during the study, are collected and reported to the FDA, appropriate IRB(s), and CSL Behring LLC. in accordance with CFR 312.32 (IND Safety Reports).

Adverse Event Reporting Period

The study period during which all AEs and SAEs must be reported begins after informed consent is obtained and initiation of study treatment and ends 150 days after the last dose of study drug

In addition to completing appropriate patient demographic and suspect medication information, the report should include the following information within the Event Description (section 5) of the MedWatch 3500A form:

- Treatment regimen (dosing frequency, combination therapy)
- Protocol description (and number, if assigned)
- Description of event, severity, treatment, and outcome if known
- Supportive laboratory results and diagnostics
- Investigator's assessment of the relationship of the adverse event to each investigational product and suspect medication

Follow-up information:

Additional information may be added to a previously submitted report by any of the following methods:

- Adding to the original MedWatch 3500A report and submitting it as follow-up
- Adding supplemental summary information and submitting it as follow-up with the original MedWatch 3500A form.
- Summarizing new information and faxing it with a cover letter including subject identifiers (i.e. D.O.B. initial, subject number), protocol description and number, if assigned, suspect drug, brief adverse event description, and notation that additional or follow-up information is being submitted (The patient identifiers are important so that the new information is added to the correct initial report)

Occasionally CSL Behring may contact the reporter for additional information, clarification, or current status of the subject for whom and adverse event was reported. For questions regarding SAE reporting, you may contact the CSL Behring Drug Safety representative noted above.

With completion of the STUDY, the INSTITUTION shall provide to CSLB via email or fax (see APPENDIX 01) the final/clinical study report within three months after completion of Study conduct or termination of this agreement.. Any

interim report is to be provided by the INSTITUTION has to be forwarded on a bi-annual basis.

In addition, the INSTITUTION shall provide a line listing/table including the causality assessment for each SAE/SAR/AR/AE/Special Situation within **five (5) working days** after closure of the database. The PARTIES will agree on the event-level detail prior to forwarding to CSLB.

Study Drug Relationship:

The investigator will determine which events are associated with the use of the study drugs. The causality assessment is the determination of whether there exists a reasonable possibility that the Study treatment caused or contributed to an adverse event:

- Not related: Temporal relationship to Study treatment administration is missing or implausible, or there is evidence of another cause.
- Possibly related: Reasonable time sequence to administration of Study treatment, but the event could also be
 explained by concurrent disease of other drugs or chemicals. Information on drug withdrawal may be lacking or
 unclear.
- Definitely related: Plausible time relationship to Study treatment administration; event cannot be explained by
 concurrent disease or other drugs or chemicals. The response to withdrawal of the drug (dechallenge) should be
 clinically plausible. The event must be definitive pharmacologically or phenomenologically, using a satisfactory rechallenge procedure if necessary.

4.5.2

Pregnancy Reporting

Should a patient or female partner of a male under treatment with a CSLB product become pregnant during the course of the STUDY, this information must be forwarded to CSLB within ten (10) calendar days. The INSTITUTION shall follow-up until outcome of pregnancy is known and potential safety concerns have been clarified. As soon as outcome of pregnancy is available to the INSTITUTION this information has to be provided to CSLB within one (1) working day.

In case of a pregnancy in the female partner of a male subject, the Investigator should obtain informed consent of the pregnant partner prior to monitoring of the pregnancy.

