3.3 Exclusion Criteria

- ✓ Multi-organ transplant (e.g. kidney and pancreas)
- √ eGFR < 30 mL/min/1.73m²
- ✓ Advanced Transplant Glomerulopathy (CG3) or advanced IFTA (ct or ci scores ≥3)
- ✓ Previous allergic reactions to monoclonal antibodies.
- ✓ Lactating or pregnant females.

- ✓ Women of child-bearing age and male partners of women of child-bearing age who are not willing or able to practice FDA-approved forms of contraception during study and for 5 months after last dose.
- ✓ HIV-positive subjects.
- ✓ Subjects who test positive for HBV by HBVeAg/DNA or HCV infection [positive Anti-HCV (EIA) and confirmatory HCV RIBA].
- ✓ Subjects with latent or active TB. Subjects must have negative Quantiferon TB gold test result.
- ✓ Recent recipients of any licensed or investigational live attenuated vaccine(s) within two months of the screening visit (including but not limited to any of the following:
 - o Adenovirus [Adenovirus vaccine live oral type 7]
 - Varicella [Varivax]
 - Hepatitis A [VAQTA]
 - Rotavirus [Rotashield]
 - Yellow fever [Y-F-Vax]
 - Measles and mumps [Measles and mumps virus vaccine live]
 - Measles, mumps, and rubella vaccine [M-M-R-II]
 - Sabin oral polio vaccine
 - Rabies vaccines [IMOVAX Rabies I.D., RabAvert])
- ✓ A significantly abnormal general serum screening lab result defined as a WBC < 3.0 X 10³/ml, a Hgb < 8.0 g/dL, a platelet count < 100 X 10³/ml, an SGOT or SGPT > 3X upper limit normal
- ✓ Individuals deemed unable to comply with the protocol.
- ✓ Subjects with active CMV or EBV infection as defined by CMV-specific serology (IgG or IgM) and confirmed by quantitative PCR with or without a compatible illness (Quantitative PCR cut off defined as having > 50 copies of CMV or EBV DNA/PCR)
- ✓ Use of investigational agents within 4 weeks of participation.
- √ History or active Inflammatory Bowel Disease or Diverticular Disease or gastrointestinal perforation
- ✓ Recent infection (within past 6 weeks of screening) requiring any antibiotic use (oral, parenteral or topical).
- ✓ Present or previous (within 5 years) malignancy except for basal cell carcinoma, fully excised squamous cell carcinoma of the skin or non-recurrent (within 5 years) cervical carcinoma-in-situ.

4. Study Design & Methods

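### Pregnancy reporting in Section 4.5.2 is not aligned with the protocol's own 5-month and 150-day post-dose windows, and its partner clause, read literally, ends when a man stops dosing

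*Protocol*

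**What the plan says.** Three parts of the protocol set a time window that bears on pregnancy.

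- **Section 4.5.2 (Pregnancy Reporting).** The people covered are named in the opening clause, "Should a patient or female partner of a male under treatment with a CSLB product". The time limit is that the person should "become pregnant during the course of the STUDY", with ten calendar days to send the report. Follow-up then runs to the outcome of the pregnancy. No post-dose period is named. The next paragraph, on the partner's consent to monitoring, refers to partners of male subjects without limiting it to men on treatment.
- **Section 3.3 (Exclusion Criteria).** Subjects must be willing and able to use "FDA-approved forms of contraception during study and for 5 months after last dose". This places the 5 months on top of the time in study.
- **Section 4.5 (Adverse Event Reporting Period).** The time for reporting AEs and SAEs, which this section terms the study period, starts once consent has been given and dosing has begun. It "ends 150 days after the last dose of study drug".

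Section 4.5 also lists, among the SAE criteria, "It results in a congenital anomaly/birth defect in a neonate/infant born to a mother exposed to the IMP".

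The schedule comes from Section 4 and Appendices A and E. Patients who stop after 6 doses have their last dose at Day 150 and a final visit at Day 365. Patients who receive 12 doses have their last dose at Day 330 and, outside the long term extension, a last visit at Day 365. Appendix E lists dosing visits and folds the Day 365 assessments into one of them, so it schedules no visit after the last extension dose.

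**The concern.** The contraception window (5 months) and the AE/SAE window (150 days) are in effect the same length and run from the same event, the last dose. The pregnancy rule uses neither. It relies on a study period that it does not define and, for partners, on the man being on treatment.

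The protocol regards the months after the last dose as a time when conception should be avoided. A pregnancy in those months is therefore one on which it should want data. Section 5.3 says that data from exposed pregnancies are too few to inform on harm. It counts 8 pregnancies exposed to clazakizumab in the completed studies, 3 of them through the father. With so few, each report has value.

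The other safety rules do not clearly stand in for this one. The visible text does not class pregnancy itself as an adverse event. The birth-defect criterion is worded for exposed mothers only. A child conceived after the last dose and carried to term would be born after the 150-day SAE period has closed. The pregnancy rule, with its follow-up to outcome, is the one that would capture such a case, so its start and end should be explicit.

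**Working it through.** The plan gives no figure to reproduce here. The check sets the windows side by side and counts days.

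**Inputs.** Last dose at Day 150 (6 doses) or Day 330 (12 doses), each ±7 days, and final visit at Day 365 ±30 days (Section 4, Appendix A). Post-dose window of 150 days (Section 4.5); 5 months (Section 3.3) is 5 × 365.25/12 = 152 days, treated here as the same. Half-life after SC dosing of 31.1 to 33.6 days (Section 2.0, Clinical Pharmacology).

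**Step 1: patients, if the study ends at the last visit.** Days covered = final visit − last dose. Days uncovered = 150 − days covered, held between 0 and 150.

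| Group | Days from last dose to last visit | Uncovered | Range with visit windows |
|---|---|---|---|
| 6 doses | 365 − 150 = 215 | 0 | 0 (178 to 252 days covered) |
| 12 doses, no extension | 365 − 330 = 35 | 150 − 35 = 115 | 78 to 150 |
| Extension | no visit scheduled after last dose | up to 150 | not applicable |

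The 12-dose range comes from 395 − 323 = 72 days covered (150 − 72 = 78 uncovered) and from 335 − 337 = −2 days covered (capped at 150 uncovered).

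**Step 2: patients, on the other readings.** If the course of the study means the Section 4.5 study period, it runs to 150 days after the last dose and 0 days are uncovered. If it means the trial as a whole, a patient is covered for as long as the trial runs. Only those dosed within 150 days of its end could fall outside.

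**Step 3: partners.** The limit here is the man's treatment status, so it does not depend on how the study period is defined. A man who stops after dose 6 is off treatment after Day 150. He must use contraception to about Day 150 + 150 = Day 300 and stays in the study to Day 365. Read literally, a pregnancy in his partner at Day 200 is outside the rule. The same holds after dose 12, in the extension, and after early discontinuation.

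**Step 4: why the window exists.** Assuming first-order decay, the fraction remaining is 0.5^(t / half-life).

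- At 35 days: 0.5^(35/31.1) = 0.458 and 0.5^(35/33.6) = 0.486, so about 46% to 49%.
- At 150 days: 0.5^(150/31.1) = 0.035 and 0.5^(150/33.6) = 0.045, so about 3.5% to 4.5%.

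These half-lives come from healthy men in a Phase 1 study and serve only as illustration.

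**Step 5: how many events to expect.** A crude rate is 8 exposed pregnancies among 888 exposed subjects (Section 2.0), or 8/888 = 0.9%. Applied to 10 subjects this gives 10 × 0.009 = 0.09 pregnancies in all, and fewer in a post-dose tail. The populations differ, so this shows only the order of magnitude.

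**The case against.** A reader might infer that pregnancies conceived after the last dose need not be reported at all. For patients, the document does not support that.

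- Section 4.5.2 never says that the study ends at a subject's last visit. The term is written in the style of a trial-level agreement, and Section 4 describes the extension as ongoing until approval or termination. On that reading a pregnancy 100 days after one subject's last dose is still within the study.
- Section 4.5 itself calls the time to 150 days after the last dose a study period, and on that reading patients are fully covered.
- For patients who stop at 6 doses, the whole 150 days lie before Day 365.
- Some of the safety-reporting text next to these sections is not in the copy reviewed, so its bearing on the question cannot be checked.

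These points stand, and they reduce the patient side to an undefined term. They do not remove it. Section 4.5 defines its period for AEs and SAEs, and Section 3.3 treats the 5 months as additional to the study.

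On partners, the best reply is that the limit to men on treatment is loose drafting: the sentence also carries the study-period limit, and the next paragraph speaks of male subjects in general. That is probably the intention. But the clause that triggers the report is the narrow one, and site staff would be entitled to apply it as written.

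Finally, very few events are expected in 10 subjects. That limits the severity, but the correction is also very small.

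**Conclusion.** The point holds as a misalignment between sections.

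- **Partners.** Read literally, the clause ends when the man stops dosing, in every group and however the study period is defined, although contraception is still required of him.
- **Patients.** The end of the reporting window is undefined. If it is the last visit, 115 of 150 days are uncovered after 12 doses without the extension (78 to 150 with visit windows), and in the extension no visit follows the last dose. If it is the Section 4.5 period or the whole trial, the gap is little or none. After 6 doses there is none on any reading.

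The day counts rest on the nominal schedule and on treating 5 months and 150 days as equal. No endpoint, analysis or sample-size figure is affected. This is a cheap improvement of minor severity, justified because it changes which safety data are collected.

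**What to change.** Reword Section 4.5.2 so that it covers any pregnancy in a subject, or in the female partner of a male subject, from the first dose until 150 days (5 months) after the last dose. Replace the limit to men on treatment with the male-subject wording that the section's next paragraph already uses. This matches the windows in Sections 3.3 and 4.5. Since 5 months is about 152 days, state the period in one unit throughout.

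At each subject's last visit, including the last extension visit, tell the subject to report a pregnancy that occurs within that period.

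With the change, the uncovered interval is 0 days for patients and partners in all groups. The cost is one sentence, one instruction at the last visit, and occasional extra pregnancy follow-up.

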4.6 Infection Prophylaxis Protocols and Viral Monitoring Post-Transplant

All study patients, regardless of their cytomegalovirus (CMV) status, receive IV ganciclovir while inpatients and valganciclovir as outpatients for 6 months post kidney transplant, with dose adjustments for renal function. Fungal prophylaxis was accomplished with fluconazole 100 mg daily for 1 month post transplant. Pneumocystis jirovecii pneumonia and bacterial prophylaxis is accomplished with trimethoprim 80 mg and sulfamethoxazole 400 mg daily for 12 months post transplant. No additional prophylaxis will be needed for patients who are enrolled in this trial more than one year from transplant.

Viral polymerase chain reaction assays for CMV, Epstein Barr virus, Parvovirus B-19, Polyoma virus BK and JC will be performed on study patients monthly for 6 months post-transplantation. Methodologies used for monitoring viral replication have been described previously ²⁵.

5 Dosing of Clazakizumab

For antibody mediated rejection: Clazakizumab will be administered at a dose of 25mg/SC every 4 weeks post pulse methylprednisolone, plasmapheresis, and high dose IVIG. If the patient proceeds to the LTE, they will receive clazakizumab 12.5 mg or 25 mg SC Q4W or Q8W.

Product Description, Storage and Administration Instructions

Clazakizumab will be provided by CSL Behring LLC.

Generic name: Clazakizumab

Active ingredient: Genetically engineered humanized anti-IL-6 mAb

Strength: 12.5 mg/mL (once the 25 mg/mL concentration was no longer available)

Excipients: L-histidine, L-histidine monohydrochloride, sorbitol, polysorbate-80, and water for injection

Appearance: Clear to slightly opaque, colorless to dark yellow-colored solution

Dosage form: Single-dose vials (25 mg/mL or 12.5 mg/mL) for injection.

Manufacturer: Ajinomoto Althea, San Diego CA

Patheon Manufacturing Services LLC, Greenville, NC

Clazakizumab vials should be stored at ≤-20°C (-4°F) with protection from light.

The drug product will be administered undiluted at a concentration of 12.5 mg/mL.

Prepared syringes may be stored for up to 24 hours in a refrigerator, 2°-8°C (36°-46°F), and up to 4 hours of the 24 hours may be at room temperature, 15°-25°C (59°-77°F). The prepared syringes should be protected from light.

Prior to administration, clazakizumab should reach room temperature by storing unrefrigerated for 30 to 60 minutes before use.

IP requests should be sent to: [contact]

